5.1.3 Subject Exclusion Criteria

The subject must be excluded from participating in the trial if the subject:

1. is under the age of legal consent, is mentally or legally incapacitated, has significant emotional problems at the time of pre-study screening visit or expected during the conduct of the study or has a history of a clinically significant psychiatric disorder which, in the opinion of the investigator, would interfere with the study procedures.
2. has evidence of decompensated liver disease manifested by the presence of or history of ascites, esophageal or gastric variceal bleeding, hepatic encephalopathy or other signs or symptoms of advanced liver disease.
3. For cirrhotics: subjects that are Child-Pugh Class B or C, or who have a Pugh-Turcotte (CPT) score >6 , must be excluded.

NOTE: To calculate the Child-Pugh score, refer to the following website: <http://www.mdcalc.com/child-pugh-score-for-cirrhosis-mortality>.

4. is coinfecting with hepatitis B virus (e.g. HBsAg positive).
5. For subjects with HIV, has a history of opportunistic infection in the preceding 6 months prior to screening. A list of these events may be found in Appendix B of the following document: <http://www.cdc.gov/mmwr/preview/mmwrhtml/00018871.htm>

6. has a history of malignancy ≤ 5 years prior to signing informed consent except for adequately treated basal cell or squamous cell skin cancer or in situ cervical cancer or carcinoma in situ; or is under evaluation for other active or suspected malignancy.
7. has cirrhosis and liver imaging within 6 months of Day 1 showing evidence of hepatocellular carcinoma (HCC) or is under evaluation for HCC.

NOTE: If liver imaging within 6 months prior to Day 1 is not available, imaging is required during screening.

8. is taking or plans to take any of the prohibited medications listed in Section 5.5 of the protocol or is taking herbal supplements, including but not limited to St. John's Wort (*Hypericum perforatum*), from 2 weeks prior to Day 1 through 2 weeks after the study treatment period.
9. is currently participating or has participated in a study with an investigational compound within 30 days of signing informed consent and is not willing to refrain from participating in another such study during the course of this study.
10. Has, in the opinion of the investigator, clinically-relevant drug or alcohol abuse within 12 months of screening.
11. is a female and is pregnant or breast-feeding, or expecting to conceive or donate eggs from at least 2 weeks prior to Day 1 through at least 14 days after the last dose of study drug, or longer if dictated by local regulations, OR is a male subject who is expecting to donate sperm or planning to impregnate female partner(s) from at least 2 weeks prior to Day 1 through 14 days after the last dose of study drug, or longer if dictated by local regulations.

NOTE: After treatment allocation, female subjects should avoid conceiving or donating eggs and male subjects should avoid impregnating a partner or donating sperm for at least 14 days after taking the last dose of study drug.

12. has any of the following conditions:
 - a. Organ transplants (including hematopoietic stem cell transplants) other than cornea and hair.
 - b. Poor venous access that precludes routine peripheral blood sampling required for this trial.
 - c. Subject with a history of gastric surgery (e.g., stapling, bypass) or subject with a history of malabsorption disorders (e.g., celiac sprue disease).
 - d. Any clinically significant cardiac abnormalities/dysfunction, including but not limited to: unstable angina, unstable congestive heart failure, and unstable arrhythmia.
 - e. History of a medical/surgical condition that resulted in hospitalization within the 3 months prior to enrollment, other than for minor elective procedures.
 - f. Medical/surgical conditions that may result in a need for hospitalization during the period of the study.

- g. Any medical condition requiring, or likely to require, chronic systemic administration of corticosteroids, TNF antagonists, or other immunosuppressant drugs during the course of the trial.
- h. Any condition, pre-study laboratory or ECG abnormality or history of any illness, which, in the opinion of the investigator, might confound the results of the study or pose additional risk in administering the study drugs to the subject.
- i. A life-threatening SAE during the screening period.
- j. Evidence of history of chronic hepatitis not caused by HCV, including but not limited to drug-induced hepatitis, hemochromatosis, Wilson’s disease, α 1-antitrypsin deficiency, alcoholic liver disease and autoimmune hepatitis.

NOTE: Subjects with history of acute non-HCV-related hepatitis, which resolved >6 months before study entry, can be enrolled.

13. has exclusionary laboratory values at the screening visit as listed in [Table 8](#).

NOTE: If any of the laboratory exclusion criteria below in [Table 8](#) are met, the site may have the abnormal value retested one time.

Table 8 Laboratory Exclusion Criteria

Laboratory Assessment	Exclusionary Values
Creatinine Clearance (estimated glomerular filtration rate, eGFR) ¹	<50 mL/min/1.73 m ²
Hemoglobin	<10 g/dL
Platelets	<50 × 10 ³ /μL
Total Bilirubin	>2.0 mg/dL unless history of Gilbert's disease (If Gilbert’s disease is the proposed etiology, this must be documented in the subject’s chart)
Serum Albumin	<3.0 g/dL
INR	>1.7 unless subject has a stable INR on an anticoagulant regimen
ALT	>10× ULN
AST	>10× ULN
¹ Creatinine clearance will be evaluated as an estimated GFR (eGFR) based on the modification of diet in renal disease (MDRD) equation: $\text{eGFR (mL/min/1.73 m}^2\text{)} = 175 \times (\text{Scr, std})^{-1.154} \times (\text{Age})^{-0.203} \times (0.742 \text{ if female}) \times (1.212 \text{ if black})$ Scr, std: serum creatinine measured with a standardized assay	

14. Is or has an immediate family member (e.g., spouse, parent/legal guardian, sibling or child) who is investigational site or sponsor staff directly involved with this trial.

5.2 Trial Treatment(s)

The treatment to be used in this trial is outlined in [Table 9](#).

Table 9 Trial Treatment for Each Arm

Drug	Dose/Potency	Dose Frequency	Route of Administration	Regimen/Treatment Period	Use
MK-3682	450mg (3 x 150mg tablet)	QD	Oral	12 weeks	Experimental
MK-8408	60mg (6 x 10mg capsule)	QD	Oral	12 weeks	Experimental

The first dose of trial treatment will be administered at the trial site at Visit 2 (Day 1). The doses to be taken at other visits at which a pre-dose PK sample is to be collected will also be administered at the trial site. All other dosing will be performed by the subject (i.e., unsupervised at his/her home) in the morning at approximately the same time each day for MK-3682 and MK-8408.

The investigator shall take responsibility for and shall take all steps to maintain appropriate records and ensure appropriate supply, storage, handling, distribution and usage of trial treatments in accordance with the protocol and any applicable laws and regulations.

5.2.1 Dose Selection/Modification

5.2.1.1 Dose Selection (Preparation)

The rationale for selection of doses to be used in this trial is provided in Section 4.0 – Background & Rationale. There are no specific calculations or evaluations required to be performed in order to administer the proper dose to each subject.

5.2.1.2 Dose Modification (Escalation/Titration/Other)

Dose modification of MK-3682 or MK-8408 is not permitted. See Section 5.2.2 for instructions if for any reason MK-3682 or MK-8408 needs to be interrupted. For any other dose modifications that occur, consult the Sponsor Protocol team.

5.2.2 Timing of Dose Administration

All doses of MK-3682 and MK-8408 should be taken on an empty stomach after an overnight fast, at least 1 hour before the morning meal. Study medications should be taken with water but without food. In addition, subjects should fast overnight prior to reporting to the study site for dosing on Treatment Day 1 (Visit 2) and for all other visits at which a pre-dose PK sample is to be collected. For study visits after Visit 2, if there are cases in which a morning visit is not feasible and a subject is seen in the afternoon, the subject should take their study medication in the morning, after an overnight fast, as per their regular schedule; PK samples will still be collected during these visits.

If a subject misses a dose of MK-3682 or MK-8408 and it is less than 8 hours before the next dose, the missed dose should be skipped and the normal dosing schedule resumed. Subjects should not double the next dose in order to compensate for what has been missed.

If a subject misses a dose of MK-3682 or MK-8408 and it is greater than 8 hours before the next dose, the missed dose should be taken at least 2 hours after last meal and 1 hour before next meal and the normal dosing schedule resumed.

If for any reason MK-3682 or MK-8408 needs to be interrupted, the entire regimen should be interrupted and can be interrupted for up to 3 days. If the interruption lasts for more than 3 days, consult the Sponsor Protocol team.

5.2.3 Trial Blinding

This is an open-label trial; therefore, the Sponsor, investigator and subject will know the treatment administered.

5.3 Randomization or Treatment Allocation

All subjects will receive a treatment regimen of MK-3682 (450mg) + MK-8408 (60mg) co-administered concomitantly as separate medications once-daily for 12 weeks. Subjects will be assigned to treatment arms based on genotype.

Documentation of treatment period entry will occur centrally using a computer generated allocation schedule to assign a treatment/allocation number.

5.4 Stratification

Although there is no randomization, subjects are classified (stratified) by genotype to determine assignment to treatment arm by design. No other stratification based on age, sex, or other characteristics will be used in this trial.

5.5 Concomitant Medications/Vaccinations (Allowed & Prohibited)

Medications or vaccinations specifically prohibited in the exclusion criteria are not allowed during the ongoing trial. If there is a clinical indication for any medication or vaccination specifically prohibited during the trial, discontinuation from trial therapy or vaccination may be required. The investigator should discuss any questions regarding this with the Sponsor Clinical Director. The final decision on any supportive therapy or vaccination rests with the investigator and/or the subject's primary physician. However, the decision to continue the subject on trial therapy or vaccination schedule requires the mutual agreement of the investigator, the Sponsor and the subject.

It is important for investigators to review each medication (prescription and non-prescription) the subject is taking before starting the study and at each study visit.

- At each visit, subjects should be questioned about any new drug they are taking or have taken since the last visit.
- To minimize the risk of adverse drug interactions, every effort should be made to limit the number of concomitant drugs to those that are truly essential.
- Drugs known to be hepatotoxic (i.e., drugs with a warning of hepatotoxicity in the package insert) should be avoided during the dosing period. Investigators are encouraged to review each medication for potential hepatotoxicity by searching the www.livertox.nih.gov website.

Specific restrictions for concomitant therapy during the course of the trial are listed. These are based on the current known metabolism of the drugs as described.

Restrictions may be removed if indicated by emergent data from drug-drug interaction trials. Any medications/therapies no longer contraindicated will be communicated to the site by an administrative letter.

The following medications/therapies are not permitted from 2 weeks prior to Day 1 through 2 weeks after the study treatment period.

Known hepatotoxic drugs, including but not limited to:

- etifoxine
- isoniazid
- nitrofurantoin

Herbal supplements

Antiarrhythmic agents (including but not limited to amiodarone, quinidine, bepridil, disopyramide, flecainide, systemic lidocaine, mexiletine, propafenone)

Strong inhibitors of CYP3A, including but not limited to:

- clarithromycin
- telithromycin
- itraconazole
- ketoconazole
- nefazodone

Strong and moderate CYP3A inducers, including but not limited to:

- anti-infectives: nafcillin, rifampin
- anticonvulsants: carbamazepine, phenytoin, phenobarbital
- bosentan
- modafinil
- St. John's Wort

Gastric acid modifiers

- H2 blockers
- proton-pump inhibitors

Note: antacids, such as calcium carbonate or aluminum hydroxide-based product, will be allowed during the study, but it is recommended they be taken either 4 hours before or after dosing of MK-3682 and MK-8408 (see Allowed Medication below)

HIV medications (note that not all prohibited HIV medications are listed):

- efavirenz
- etravirine
- nevirapine
- ritonavir
- all boosted and unboosted HIV protease inhibitors

Note: the only permitted HIV medications are tenofovir, abacavir, lamivudine, emtricitabine, raltegravir, dolutegravir and rilpivirine

HMG-CoA reductase inhibitors (statins):

- rosuvastatin greater than 10 mg (see Allowed Medications below)
- atorvastatin, simvastatin, lovastatin, or fluvastatin greater than 20 mg (see Allowed Medications below)

In general, P-gp substrates with narrow therapeutic ranges (e.g., digoxin and colchicine) are not prohibited, but their levels have the potential to be increased. Therefore, subjects taking these medications should be monitored closely.

Investigational agents are not permitted.

Systemic corticosteroids (dose equivalent to ≥ 10 mg prednisone per day, except in the case of rapid steroid tapers < 1 week in duration) are not permitted.

Allowed Medications:

The following concomitant medications are allowed in this study:

Antihypertensives:

- ACE inhibitors/ARB: enalapril, captopril, lisinopril, ramipril, valsartan, losartan, telmisartan
- beta blockers: atenolol, metoprolol, propranolol
Note: for other beta blockers, please consult with the Sponsor
- calcium-channel blockers: amlodipine, diltiazem, verapamil
Note: for other calcium-channel blockers, please consult with the Sponsor
- hydralazine, clonidine, minoxidil, isosorbide nitrates

Anemia: erythropoetin

Diuretics: hydrochlorothiazide, furosemide, spironolactone, triamterene

Hypoglycemic agents: insulin, sitagliptin, glipizide, metformin

Contraceptives: oral contraceptive pills, progesterone injects, intrauterine devices

Antidepressants/anxiolytics: citalopram, paroxetine, duloxetine, escitalopram, fluoxetine, bupropion, trazodone, diazepam, clonazepam, temazepam, lorazepam

Acid reflux:

- antacids (stomach acid neutralizers, such as calcium carbonate or aluminum hydroxide-based products) are permitted, but it is recommended that they be taken either 4 hours before or after dosing of MK-3682 and MK-8408

HMG-CoA reductase inhibitors (statins):

- pravastatin and pitavastatin: may be coadministered without dose adjustment
- rosuvastatin: use the lowest possible effective dose of rosuvastatin, but do not exceed a daily dose of 10 mg
- atorvastatin, simvastatin, fluvastatin, lovastatin: use the lowest possible effective dose of atorvastatin, but do not exceed a daily dose of 20 mg

Anti-coagulants: warfarin, heparin, low molecular weight heparin, aspirin, fondaparinux, desirudin, acenocoumarol

Opiate substitution therapy: Subjects on stable doses of methadone or buprenorphine/naloxone may be enrolled in this study, if not excluded under Exclusion Criterion 10 in Section 5.1.3.

Given that this list is not comprehensive, the investigator should use his/her medical judgment when a subject presents with a medication not on the list or consult with the Sponsor.

5.6 Rescue Medications & Supportive Care

No rescue or supportive medications are specified to be used in this trial.

5.7 Diet/Activity/Other Considerations

MK-3682 and MK-8408 should be taken on an empty stomach after an overnight fast and at least 1 hour before the morning meal. Study medication should be taken with water but without food.

5.8 Subject Withdrawal/Discontinuation Criteria

Subjects may withdraw consent at any time for any reason or be dropped from the trial at the discretion of the investigator should any untoward effect occur. In addition, a subject may be withdrawn by the investigator or the Sponsor if enrollment into the trial is inappropriate, the trial plan is violated, or for administrative and/or other safety reasons. Specific details regarding discontinuation or withdrawal procedures; including specific details regarding withdrawal from Future Biomedical Research, are provided in Section 7.1.4 – Other Procedures.

A subject must be discontinued from the trial if:

- The subject or legal representative (such as parent or legal representative) withdraws consent.

A subject must be discontinued from treatment but continue to be monitored in the trial for any of the following reasons:

[Table 10](#) provides reasons why a subject must be discontinued from treatment but should continue to be monitored in the trial, as well as reasons why a subject must be discontinued from treatment and the trial.

Table 10 Discontinuation Scenarios

Reason for Discontinuation Scenario	Action
The subject has a medical condition or personal circumstance which, in the opinion of the investigator and/or Sponsor, places the subject at unnecessary risk through continued participation in the trial or does not allow the subject to adhere to the requirements of the protocol.	Discontinue from Treatment and Trial
Subject meets criteria for HCV virologic breakthrough or rebound (see Section 4.2.3.1.1.2)	Discontinue from Treatment (should continue to monitor in the trial)
Subject becomes pregnant during the trial.	Discontinue from Treatment (should continue to monitor in the trial)
A physician investigator feels it is in the best interest of the subject to discontinue.	Discontinue from Treatment (should continue to monitor in the trial)
The subject's ALT or AST increases to >500 IU/L and is confirmed with repeat test within one week.	Discontinue from Treatment (should continue to monitor in the trial)
The subject's ALT or AST increases to >3x the nadir value, is >3x ULN (confirmed with repeat test within one week), and there is a simultaneous increase in total bilirubin > 2x ULN and/or INR is increased from the baseline value and is >1.5 (unless the subject is on anticoagulation).	Discontinue from Treatment (should continue to monitor in the trial)
The subject's ALT or AST increases to >3x nadir, is >3x ULN (confirmed with repeat test within one week), and is temporally associated with signs or symptoms of liver inflammation that are of moderate or severe intensity and deemed by the investigator to be at least possibly related to study therapy.	Discontinue from Treatment (should continue to monitor in the trial)
The subject's serum creatinine increases to Grade 3 or higher (>1.8x upper limit of normal), confirmed with repeat test within one week.	Discontinue from Treatment (should continue to monitor in the trial)
The subject's creatinine clearance (eGFR) decreases to <30 mL/min/1.73 m ² , confirmed with repeat test within 1 week. Creatinine clearance will be evaluated as an estimated GFR (eGFR), based on the modification of diet in renal disease (MDRD) equation: $eGFR \text{ (mL/min/1.73 m}^2\text{)} = 175 \times (\text{Scr, std})^{-1.154} \times (\text{Age})^{-0.203} \times (0.742 \text{ if female}) \times (1.212 \text{ if black})$ Scr, std: serum creatinine measured with a standardized assay	Discontinue from Treatment (should continue to monitor in the trial)
The subject has a Grade 4 laboratory AE, or a life-threatening clinical AE, or an AE that results in or prolongs an existing in-subject hospitalization, that is assessed to be a study drug-related laboratory or clinical AE.	Discontinue from Treatment (should continue to monitor in the trial)
SAE assessed by the physician investigator as possibly or probably related to study medication. Investigator may continue the subject in the trial, if it is deemed to be in the best interest of the subject to stay on the study treatment after consultation with Sponsor.	May Discontinue from Treatment (should continue to monitor in the trial)
Failure to comply with the dosing, evaluations, or other requirements of the trial.	May Discontinue from Treatment (should continue to monitor in the trial)

NOTE: Clinical management of HIV-1 virologic failure will be handled by site investigators according to current HIV treatment guidelines and local standard of care. Subjects with HIV virologic failure may continue in the study unless there is a requirement for prohibited concomitant medications (see Section 5.5) to construct a new HIV treatment regimen.

Discontinuation from treatment is “permanent.” Once a subject is discontinued, he/she shall not be allowed to restart treatment.

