7.2.3 Immediate Reporting of Adverse Events to the Sponsor

7.2.3.1 Serious Adverse Events

A serious adverse event is any adverse event occurring at any dose or during any use of Sponsor's product that:

- Results in death;
- Is life threatening;
- Results in persistent or significant disability/incapacity;
- Results in or prolongs an existing inpatient hospitalization;
- Is a congenital anomaly/birth defect;
- Is an other important medical event.

Note: In addition to the above criteria, adverse events meeting either of the below criteria, although not serious per ICH definition, are reportable to the Sponsor in the same timeframe as SAEs to meet certain local requirements. Therefore, these events are considered serious by the Sponsor for collection purposes.

- Is a cancer;
- Is associated with an overdose.

Refer to [Table 14](#) for additional details regarding each of the above criteria.

For the time period beginning when the consent form is signed until treatment allocation/randomization, any serious adverse event, or follow up to a serious adverse event, including death due to any cause, that occurs to any subject must be reported within 24 hours to the Sponsor if it causes the subject to be excluded from the trial, or is the result of a

protocol-specified intervention, including but not limited to washout or discontinuation of usual therapy, diet, placebo treatment or a procedure.

For the time period beginning at treatment allocation/randomization through 14 days following cessation of treatment, any serious adverse event, or follow up to a serious adverse event, including death due to any cause, whether or not related to the Sponsor's product, must be reported within 24 hours to the Sponsor either by electronic media or paper. Electronic reporting procedures can be found in the EDC data entry guidelines. Paper reporting procedures can be found in the Investigator Trial File Binder (or equivalent).

Additionally, any serious adverse event, considered by an investigator who is a qualified physician to be related to the Sponsor's product that is brought to the attention of the investigator at any time outside of the time period specified in the previous paragraph also must be reported immediately to the Sponsor.

All subjects with serious adverse events must be followed up for outcome.

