	Dechallenge	Was the Sponsor's product discontinued or dose/exposure/frequency reduced? If yes, did the AE resolve or improve? If yes, this is a positive dechallenge. If no, this is a negative dechallenge. (Note: This criterion is not applicable if: (1) the AE resulted in death or permanent disability; (2) the AE resolved/improved despite continuation of the Sponsor's product; (3) the trial is a single-dose drug trial; or (4) Sponsor's product(s) is/are only used one time.)
	Rechallenge	Was the subject re-exposed to the Sponsor's product in this trial? If yes, did the AE recur or worsen? If yes, this is a positive rechallenge. If no, this is a negative rechallenge. (Note: This criterion is not applicable if: (1) the initial AE resulted in death or permanent disability, or (2) the trial is a single-dose drug trial; or (3) Sponsor's product(s) is/are used only one time.) NOTE: IF A RECHALLENGE IS PLANNED FOR AN ADVERSE EVENT WHICH WAS SERIOUS AND WHICH MAY HAVE BEEN CAUSED BY THE SPONSOR'S PRODUCT, OR IF RE-EXPOSURE TO THE SPONSOR'S PRODUCT POSES ADDITIONAL POTENTIAL SIGNIFICANT RISK TO THE SUBJECT THEN THE RECHALLENGE MUST BE APPROVED IN ADVANCE BY THE SPONSOR CLINICAL DIRECTOR AND THE INSTITUTIONAL REVIEW BOARD/INDEPENDENT ETHICS COMMITTEE.
	Consistency with Trial Treatment Profile	Is the clinical/pathological presentation of the AE consistent with previous knowledge regarding the Sponsor's product or drug class pharmacology or toxicology?
The assessment of relationship will be reported on the case report forms /worksheets by an investigator who is a qualified physician according to his/her best clinical judgment, including consideration of the above elements.		
Record one of the following:	Use the following scale of criteria as guidance (not all criteria must be present to be indicative of a Sponsor's product relationship).	
Yes, there is a reasonable possibility of Sponsor's product relationship.	There is evidence of exposure to the Sponsor's product. The temporal sequence of the AE onset relative to the administration of the Sponsor's product is reasonable. The AE is more likely explained by the Sponsor's product than by another cause.	

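### Table 10 overlaps: a drug-related life-threatening or hospitalising AE meets both a row that requires treatment to stop and a row that leaves stopping to discretion

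*Combined protocol and SAP*

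**What the plan says.** Section 5.8 introduces its list with "A subject must be discontinued from treatment but continue to be monitored in the trial for any of the following reasons" and then presents Table 10.

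One row of Table 10 begins "The subject has a Grade 4 laboratory AE, or a life-threatening clinical AE, or an AE that results in or prolongs an existing" and, for the hospitalisation arm and the relatedness condition, continues as "an AE that results in or prolongs an existing in-subject hospitalization, that is assessed to be a study drug-related laboratory or clinical AE". Its action is to discontinue from treatment while monitoring continues. This is called the mandatory row below.

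The next row is triggered by an "SAE assessed by the physician investigator as possibly or probably related to study medication". It adds: "Investigator may continue the subject in the trial, if it is deemed to be in the best interest of the subject", and the sentence goes on to refer to staying on study treatment after the Sponsor has been consulted. The action column begins "May Discontinue from Treatment (should continue to monitor in the trial". This is called the discretionary row below.

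The note after the table makes treatment discontinuation permanent, with no restart.

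Section 7.2.3.1 lists life-threatening events among the SAE criteria, along with any AE that "Results in or prolongs an existing inpatient hospitalization". In Table 14 (Section 7.2.4) causality is recorded as one of two answers: "Yes, there is a reasonable possibility of Sponsor's product relationship", or the corresponding No.

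**The concern.** The events in the mandatory row are among the most serious that the trial can attribute to study drug. An investigator facing one of them finds two adjacent rows that both describe it. One requires treatment to stop. The other leaves stopping open and mentions continued dosing expressly.

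Two things are at stake. The first is the subject's exposure, because a stop cannot be reversed. The second is a reported result: Section 8.6.2 places AE leading to discontinuation in the first safety tier, with a point estimate and 95% CI for each arm and for all genotypes combined. If similar events are handled under different rows, that proportion partly reflects how the table was read.

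**Working it through.** The plan gives no figure on this point, so the main check compares the text of the two rows.

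**Inputs**

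| | Mandatory row | Discretionary row |
|---|---|---|
| Trigger (Table 10) | Grade 4 laboratory AE, life-threatening clinical AE, or AE causing or prolonging hospitalisation | Any SAE |
| Relatedness wording | Study drug-related | Possibly or probably related |
| Action | Stop treatment, keep monitoring | May stop treatment, keep monitoring; may stay on treatment after Sponsor consultation |
| Exclusion of the other row's events | None written | None written |

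**Step 1: do the triggers overlap?** Section 7.2.3.1 makes every life-threatening AE an SAE and every AE that causes or prolongs hospitalisation an SAE. So every drug-related clinical event of these two kinds falls in both rows. The mandatory row stands alone only for a Grade 4 laboratory AE that meets no SAE criterion. The discretionary row stands alone for the remaining related SAEs, such as disability, congenital anomaly, other important medical events, and the cancer and overdose-associated events that the Sponsor treats as serious.

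**Step 2: does the causality wording separate them?** It could do so only if the trial graded relatedness. Table 14 records Yes or No to a reasonable possibility. No recorded field distinguishes a drug-related event from one that is possibly or probably related.

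**Step 3: do the actions conflict?** Stopping treatment is consistent with both rows. Continuing is allowed by the discretionary row and not by the mandatory row. The conflict is therefore between a requirement and an option, for the same event.

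**Step 4: does the introduction settle it?** It says that treatment must be discontinued for the reasons in the list. Two rows of the table then say that treatment may be discontinued: the discretionary row and the non-compliance row. The introduction does not describe the table that it introduces, so it gives no clear precedence.

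**Step 5: how many subjects?** The documents give no expected count. The nearest figure is in Section 4.1.2.2.2: Part A of PN011 and PN012 reported no drug-related SAE, and no discontinuation due to an AE, in 240 subjects. With zero events the exact two-sided 95% upper limit is 1 − 0.025^(1/n). For n = 240 this is 1 − 0.025^(1/240) = 1.5%, and 0.0153 × 250 = 3.8, or about 4 subjects in a trial of this size. Part A used 8-week three-drug regimens in treatment-naïve, non-cirrhotic subjects, so this is indicative only.

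**Step 6: how much could a few subjects move the reported interval?** The same formula reproduces Table 20 for zero events: 1 − 0.025^(1/25) = 13.7% and 1 − 0.025^(1/50) = 7.1%. For two events Table 20 gives upper bounds of 26.0% (n = 25) and 13.7% (n = 50). As an illustration, if two subjects in one arm were classed differently, starting from none, the upper bound for that arm would rise from 13.7% to 26.0%, or from 7.1% to 13.7%.

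**The case against.** The strongest defence is that the specific row governs the general one. The mandatory row names particular events, and the discretionary row then covers the other related SAEs, so both keep a purpose. This is a plausible account of the intent, but it is not written. The discretionary row says SAE, not other SAE, and its permission to stay on treatment could also be read as an exception to the row directly above it.

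Several other objections stand and limit the point:

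- A reader might infer that the rows give opposite instructions, so that a site complies equally well by stopping or by continuing. The text does not support that. Continuing satisfies the protocol only if the discretionary row is taken to override the mandatory one, and nothing says that it does.
- A reader might infer that sites will diverge freely. Continuation requires Sponsor consultation, and SAEs from allocation through 14 days after treatment are reported to the Sponsor within 24 hours (Section 7.2.3.1). This central step limits divergence between sites, although it does not tell the Sponsor which row to apply.
- The other first-tier parameters (any AE, drug-related AE, SAE, serious drug-related AE, laboratory ECIs) are not defined by which row was used.
- The mismatch in causality terms does not create the conflict by itself. It removes one way of resolving it.

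**Conclusion.** The inconsistency is real and should be corrected. Every drug-related life-threatening or hospitalising clinical AE meets two rows of Table 10 with different actions, and the documents give no rule for choosing between them. The conclusion rests only on the SAE definition in Section 7.2.3.1 and the binary causality record in Table 14.

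The consequence is limited. The row applied could change a subject's exposure and the count of AEs leading to discontinuation. The number affected is probably small and may be zero. The upper figure of about 4 of 250 assumes that the Part A experience carries over to a 12-week two-drug regimen in a broader population, which the documents do not show.

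Two larger readings are not supported. A reader might take the threshold of 12 subjects (~5%) in Section 5.11.2 as the number at risk of conflicting instructions. It is a trial-termination limit that pools transaminase, creatinine, eGFR and Grade 4 laboratory criteria with clinical events, and it is not an expected count. A reader might also infer that a stop determines the subject's SVR12 result. Stopping treatment is not leaving the trial: Section 7.1.5.4 sends these subjects on to the follow-up visits. The failure imputation in Section 8.6.1 applies to data missing after premature study discontinuation, not to stopping treatment as such. Shorter exposure may influence SVR12, but SVR12 is still measured.

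**What to change.** Reconcile the two rows so that each drug-related SAE has exactly one action. State in the discretionary row whether it includes or excludes the events named in the mandatory row. Word both rows in Table 14's Yes/No causality terms, and align the introductory sentence of Section 5.8 with a table that contains both required and optional stops. Which action applies is for the sponsor to decide.

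The cost is a wording change to two table rows and one sentence, with no new data. The documents do not say whether dosing is complete, but Amendment 04 refers to subjects already in long-term follow-up. If no subject remains on treatment, the equivalent step is to identify in the CSR any subject who met both rows and the action that was taken.
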